Endoscopic sinus surgery (ESS) to change quality of life for adults with recurrent rhinosinusitis

Statistical analysis plan

04.09.2020

Statistical methods for primary and secondary outcomes

To describe the data the following methods will be used. Data for normal distribution will be presented as mean and standard deviation (SD). Variables for skewed distributions will be described as median and interquartile range. Categorical variables will be expressed as frequencies with percentages.

The primary and secondary outcomes, measures and planned statistical analyses are displayed in Table 2. Our primary outcome is the difference between the average change in SNOT-22 scores from baseline to six months between the ESS and control groups. If the average baseline scores happen to be different between the two groups, comparison of the follow-up scores or change scores will lead to under- or overestimation of the treatment effect. Therefore, the analysis of covariance will be used where possible baseline imbalances are controlled for. The estimate for difference between the means will be calculated with 95% confidence intervals. Statistical significance will not be presented for secondary outcomes to avoid multicomparison problem.

Table 2. Variables, measures and planned statistical analyses. ESS= endoscopic sinus surgery, SNOT-22= Sinonasal outcome test quality of life questionnaire, RAND 36 = Research and Development 36 Item Health Survey, MIC = minimal clinically important change, CI = confidence interval, NNT= number needed to treat

Variable/Outcome	Hypothesis	Outcome measure	Method of analysis
------------------	------------	-----------------	--------------------

Primary outcome	ESS improves outcome from baseline to 6 months	Difference between the mean SNOT-22 change scores of ESS and control group	Analysis of covariance, estimate for difference between means with 95% CI (adjusted age (≤ 50 vs. > 50 years), sex and allergy status (yes vs, no))
Secondary outcomes			
General QoL change	Improvement occurs	Difference between the mean RAND-36 change scores of ESS and control group	Analysis of covariance
Proportion benefiting	Improvement occurs	Difference in proportions benefiting (SNOT-22 $>$ MIC) in ESS and control group	Chi-squared test, Risk ratio with 95% CI, NNT
No. of episodes, visits, antibiotic courses, sick days	Improvement occurs	Difference in number of episodes, visits, antibiotic courses and sick days in ESS and control group	Difference in means with 95% CI
No. of symptomatic days	Improvement occurs	Difference in no. of days with nasal obstruction, nasal discharge, facial pain/pressure, and fever in ESS and control group	Difference in means with 95% CI
No. of postoperative complications	Improvement occurs	Frequency of postoperative synechia formations, infections, nasal pain, bleeding,	Number (%)

and orbital and
intracranial
complications

Methods for additional analyses (e.g. subgroup and adjusted analyses)

We plan to conduct two subgroup analyses. We know that both age and sex will probably affect quality of life and medical care seeking. Firstly, we will compare the estimates for difference between the mean SNOT-22 scores between the ESS and control groups both in males and females. Secondly, we will do the same analysis in participants aged ≤ 50 and > 50 years of age. We anticipate that the treatment effect will be larger among both females and younger participants.

If there is imbalance in baseline variables (age, sex, allergy status) between groups, we also perform adjusted analyses by including the following baseline variables in the analysis of covariance: age (≤ 50 vs. > 50 years), sex, and allergy status (yes vs. no).

Methods in analysis to handle protocol non-adherence and any statistical methods to handle missing data

An “as randomised” analysis is performed which retains participants in the group to which they were originally allocated (intention to treat principle). Outcome data obtained from all participants are included in the data analysis, regardless of protocol adherence. Per protocol analysis will be performed as sensitivity analysis. In case there is missing data on the primary outcome, a multiple imputation method will be used.

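### The SAP describes two different primary SNOT-22 models (age, sex and allergy always in, or added only if imbalanced), and neither lists baseline SNOT-22 as a covariate

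*SAP*

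**What the plan says.** The SAP speaks to the primary model in three places.

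- **Statistical methods for primary and secondary outcomes.** The outcome is defined as a change score: "Our primary outcome is the difference between the average change in SNOT-22 scores from baseline to six months between the ESS and control groups". ANCOVA is justified by possible differences in mean baseline score, because in that case "comparison of the follow-up scores or change scores will lead to under- or overestimation of the treatment effect". The conclusion is general: "Therefore, the analysis of covariance will be used where possible baseline imbalances are controlled for". No covariate is named.
- **Table 2, primary-outcome row.** The method is ANCOVA with an "estimate for difference between means with 95% CI (adjusted age (≤ 50 vs. > 50 years), sex and allergy status (yes vs, no". The adjustment is unconditional, and baseline SNOT-22 is not in the list.
- **Methods for additional analyses.** "If there is imbalance in baseline variables (age, sex, allergy status) between groups, we also perform adjusted analyses". The variables and the age cut-point are the same as in Table 2. No criterion for imbalance is given.

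The RAND-36 row of Table 2 has the outcome measure "Difference between the mean RAND-36 change scores of ESS and control group" and the method analysis of covariance, with no covariate named.

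**The concern.** Two accounts of one model cannot both be right. Under Table 2 the three factors are part of the primary ANCOVA. Under the additional-analyses section the primary ANCOVA exists without them, and they enter a further analysis only if the groups look unbalanced. No sentence says which result is primary.

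Either covariate set is valid if fixed in advance. The difficulty is that the text leaves room to settle the matter after both results are known. The choice is not neutral on the SAP's own account: "We know that both age and sex will probably affect quality of life and medical care seeking".

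The absence of baseline SNOT-22 is a smaller, separate point. Read literally, Table 2 is a comparison of change scores adjusted for age, sex and allergy only. That leaves uncorrected the very problem the SAP gives as its reason for using ANCOVA.

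**Working it through.** **Text comparison**

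| | Table 2, primary row | Methods for additional analyses |
|---|---|---|
| Age, sex, allergy status | in the model | added to the model |
| Condition | none | only if imbalanced, no criterion |
| Status | primary | extra |
| Baseline SNOT-22 listed | no | no |

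If Table 2 governs, the conditional sentence is redundant. If the conditional sentence governs, Table 2 misstates the primary model.

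**Size of the conflict (factors in or out, baseline SNOT-22 in both models)**

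The SAP gives no sample size, SD, power or covariate effect, so it has no figure to reproduce and the inputs are assumptions. Let R² be the share of residual variance, after baseline SNOT-22, explained by the three factors.

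- SE with factors / SE without = √(1 − R²).
- SD of the difference between the two estimates, in units of the SE without factors = √R².
- The two z statistics are taken as bivariate normal with correlation √(1 − R²). Significance means |z| > 1.96.
- For power, the mean z in the model without factors is set at 2.80 (80% power, assumed).

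| Assumed R² | 2% | 5% | 10% |
|---|---|---|---|
| SE ratio | 0.990 | 0.975 | 0.949 |
| SD of difference (SE units) | 0.141 | 0.224 | 0.316 |
| No effect: either model significant | 5.66% | 6.04% | 6.48% |
| No effect: models disagree | 1.3% | 2.1% | 2.95% |
| 80% power: models disagree | 3.2% | 5.1% | 7.4% |

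Under no effect the disagreement is twice the excess over 5%. For R² = 5%, 2 × (6.04% − 5%) = 2.1%.

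A simulation with 100 per arm, baseline-to-6-month correlation 0.5, factor prevalences of 50% and 4,000 runs (all assumed) gave either-model error of 5.6%, 6.2% and 6.0%, with Monte Carlo SE about 0.4 percentage points. A second, with 50 per arm, correlations 0.3 to 0.7 and each factor shifting the outcome by 0.3 SD, gave 5.9% to 6.9%. Both are in line with the formula.

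**Size under the literal Table 2 list (no baseline SNOT-22)**

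Let ρ be the baseline-to-6-month correlation and k the 6-month SD divided by the baseline SD. Both are assumed, and where the factors relate to the score they are values within factor levels.

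- SE of the change-score model / SE of ANCOVA with baseline = √[(1 + k² − 2ρk) / (k²(1 − ρ²))].
- Shift of the change-score estimate from the ANCOVA estimate, per point of chance baseline gap = ρk − 1.

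For example, with ρ = 0.5 and k = 1: √[(1 + 1 − 1) / 0.75] = 1.155, and the shift is 0.5 − 1 = −0.50.

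| k | SE ratio at ρ = 0.3, 0.5, 0.7 | Shift at ρ = 0.3, 0.5, 0.7 |
|---|---|---|
| 0.7 | 1.549, 1.466, 1.429 | −0.79, −0.65, −0.51 |
| 1.0 | 1.240, 1.155, 1.085 | −0.70, −0.50, −0.30 |
| 1.5 | 1.071, 1.018, 1.001 | −0.55, −0.25, +0.05 |

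**The case against.** The strongest reply is that this is loose drafting of one plan. The parenthesis in Table 2 and the conditional sentence use identical variables and cut-points, so the parenthesis may be shorthand for the extra analysis. Baseline score is the only baseline quantity in the argument for ANCOVA, so a fair reader would take it as a covariate. The SAP nowhere says the more favourable result will be chosen; saying that adjusted analyses are also performed suggests both would be reported. The error figures of 5.7% to 6.5% need an analyst who picks whichever model is significant.

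Much of this stands. Baseline SNOT-22 was very probably intended, so the literal-reading figures should not drive the severity. The RAND-36 row is a wording note: it is a secondary outcome, and the SAP will not present significance for those. The imbalance trigger governs an additional analysis and does not by itself alter the primary estimate. The inflated error is a limit on what the ambiguity permits, not a description of what the SAP intends.

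The shorthand reading does not remove the conflict. Table 2 does not state it, and it places the adjustment in the primary row without condition. A protocol not shown here could specify the model, but it could not make these two SAP statements agree.

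**Conclusion.** The point holds and should be fixed before analysis. The SAP gives two incompatible descriptions of the primary model and does not say which prevails. For assumed R² of 2% to 10%, including the factors lowers the SE by about 1% to 5%, and the two estimates typically differ by 0.14 to 0.32 SE. The models reach different conclusions at 5% in about 1% to 3% of trials with no effect, and in about 3% to 7% of trials with an assumed 80% power. This is modest, but avoidable.

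Leaving baseline SNOT-22 unnamed is secondary. It would matter more only under the less likely literal reading, where with equal SDs and correlation 0.3 to 0.7 the SE would be 8% to 24% larger and the estimate would move 0.3 to 0.7 points per point of baseline gap. That result is sensitive to the SD ratio, and the SAP gives neither the SDs nor the correlation.

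**What to change.** 1. In the primary row of Table 2, state one model: ANCOVA of 6-month SNOT-22 (or its change) on treatment group, with baseline SNOT-22 as a continuous covariate.
2. Decide now whether age, sex and allergy status are always in that model or are always added in a prespecified sensitivity analysis, and say which result is primary.
3. Delete the imbalance condition from the additional-analyses section so that it agrees with Table 2.
4. In the RAND-36 row, name baseline RAND-36 as the covariate.

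The cost is wording in two table rows and one sentence. No new data are needed, because baseline scores are already required to compute change.

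### The SAP justifies ANCOVA by chance baseline differences but never names baseline SNOT-22 as a covariate, and Table 2's covariate list, read as complete, contradicts that reason

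*SAP*

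**What the plan says.** Under the heading on statistical methods for primary and secondary outcomes, the SAP defines the endpoint: "Our primary outcome is the difference between the average change in SNOT-22 scores from baseline to six months between the ESS and control groups". It then gives its reason for the method, on the condition that mean baseline scores turn out unequal in the two arms: "comparison of the follow-up scores or change scores will lead to under- or overestimation of the treatment effect". The next sentence draws the conclusion: "Therefore, the analysis of covariance will be used where possible baseline imbalances are controlled for". That sentence names no covariate.

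Table 2 does. Its primary-outcome row takes the SNOT-22 change score as the measure and specifies ANCOVA "adjusted age (≤ 50 vs. > 50 years), sex and allergy status (yes vs, no".

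The RAND-36 row has the measure "Difference between the mean RAND-36 change scores of ESS and control group" and gives ANCOVA as the method with no covariate at all.

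The section on additional analyses adds two things. For the subgroups, "we will compare the estimates for difference between the mean SNOT-22 scores between the ESS and control groups both in males and females", and likewise by age; no covariate is mentioned. For adjustment, "If there is imbalance in baseline variables (age, sex, allergy status) between groups, we also perform adjusted analyses", and the list that follows is again age group, sex and allergy status.

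**The concern.** ANCOVA corrects for a chance difference in baseline scores only if the baseline score is in the model. Age group, sex and allergy status do not stand in for it unless they explain most of its variation, and nothing in the SAP suggests that they do. With a change score as outcome and only those three factors as covariates, the fitted model is an adjusted change-score comparison. That is one of the two comparisons the SAP says will mislead when baseline means differ. The stated list and the stated reason therefore conflict, and they do so on the primary analysis.

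Two things are at stake. The choice between the models would be made after the data are in hand: two analysts could each claim to follow the SAP and report different primary estimates. And if the list is followed to the letter, the estimate depends on chance imbalance and is less precise than it need be.

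**Working it through.** **No figure to reproduce.** The SAP gives no sample size, SD, correlation or expected effect, so the size of the problem can only be shown under assumptions.

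**Assumptions.** Equal SD (s) at both visits; correlation r between baseline and six-month SNOT-22, taken as 0.3, 0.5 and 0.7; age group, sex and allergy status explain little of the score.

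**Shift under imbalance.** Let d be the ESS-minus-control difference in mean baseline score and T the true effect.
- Expected follow-up difference given d: T + r·d.
- Expected difference in change given d: T + r·d - d = T - (1-r)·d.
- The shift is therefore -(1-r)·d. It averages to zero over randomisations because d does. With baseline in the model the term in d is removed.

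**Precision.**
- Variance of a change score: 2(1-r)·s².
- Residual variance after baseline adjustment: (1-r²)·s².
- Ratio: 2(1-r)/(1-r²) = 2/(1+r). The CI width ratio is its square root.

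| r | Shift per point of d | d = 3 | d = 5 | Variance ratio 2/(1+r) | CI width ratio |
|---|---|---|---|---|---|
| 0.3 | -0.7 | -2.1 | -3.5 | 2/1.3 = 1.54 | 1.24 |
| 0.5 | -0.5 | -1.5 | -2.5 | 2/1.5 = 1.33 | 1.15 |
| 0.7 | -0.3 | -0.9 | -1.5 | 2/1.7 = 1.18 | 1.08 |

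The imbalances of 3 and 5 points are illustrative. If s were 20 with 40 per arm (both assumed), the SD of d would be 20 × √(2/40) = 4.5 points, so neither value would be unusual.

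**Simulation check.** 4,000 trials were simulated at each r, with 40 per arm, SD 20 and no treatment effect (all assumed). The three Table 2 factors were in both models.
- Without the baseline score, the estimate moved by -0.71, -0.51 and -0.32 points per point of imbalance at r = 0.3, 0.5 and 0.7. With it, the movement was about -0.01.
- Variance with the baseline score was 0.65, 0.74 and 0.84 of that without; the formula (1+r)/2 gives 0.65, 0.75 and 0.85.
- The mean error without the baseline score was within 0.02 points of zero, which confirms that there is no bias on average.

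**Subgroups.** The SD of d varies as 1/√n. A stratum holding half of each arm has chance imbalances √2 = 1.41 times as large, so the same omission matters more there.

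**The case against.** The strongest reply is that baseline adjustment is already implied. The only imbalance mentioned before the SAP turns to ANCOVA is in baseline scores, so the conclusion it draws must concern those scores. The RAND-36 row asks for ANCOVA without any covariate, which makes sense only if the outcome's own baseline is understood. The additional-analyses section says the three factors are also to be included if they are imbalanced, which presupposes an ANCOVA that already contains something else.

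Most of this stands as evidence of intent. It rules out a stronger reading that a reader might infer, namely that the SAP decided to leave the baseline score out. The documents show an unnamed covariate, not a decision against it.

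It does not settle what will be fitted. The sentence introducing ANCOVA names no variable. The one place where the SAP says which baseline variables it means, "If there is imbalance in baseline variables (age, sex, allergy status) between groups, we also perform adjusted analyses", lists three factors without SNOT-22. Table 2 attaches the same three to the primary analysis without any condition, and an analyst following it would be compliant.

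A reader might also infer that the SAP condemns its own primary analysis as biased. It does not. Its warning applies only if baseline means differ, and under randomisation the change-score contrast is unbiased on average.

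Finally, one might object that the subgroup text refers to scores rather than change scores. That falls away once baseline is in the model, because the treatment estimate is then the same for either outcome. What remains is that the subgroup text does not say which model is used.

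**Conclusion.** The point holds as a conflict between a stated reason and a stated covariate list on the primary analysis. Baseline SNOT-22 is never named, and Table 2 read as complete gives an analysis that does not do what the prose says ANCOVA is for.

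On that reading the cost is a conditional shift plus lost precision, not systematic bias: about -0.7 to -0.3 points per point of baseline difference, and a CI about 24% to 8% wider, over r = 0.3 to 0.7. These sizes rest on equal SDs, the assumed range of r and weak prediction by the three listed factors; the SAP supplies none of these inputs. If the analyst instead follows the apparent intent and includes the baseline score, the cost disappears. The SAP should fix that choice before the data are seen.

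The RAND-36 row and the subgroup paragraph share the gap in a milder form: they name no covariate, so they are silent where the primary row is contradictory.

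**What to change.** - **Table 2, primary row:** state that the ANCOVA of six-month SNOT-22 change includes treatment group and baseline SNOT-22 as a continuous covariate, in addition to any other listed covariates.
- **Table 2, RAND-36 row:** name the corresponding baseline RAND-36 score as a covariate.
- **Subgroup paragraph:** state that the estimates by sex and by age come from the same baseline-adjusted model as the primary analysis.
- **While editing:** make Table 2 and the additional-analyses section agree on whether age group, sex and allergy status belong to the primary model or only to the analysis triggered by imbalance. In either case, say that the baseline score is always included.

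The cost is a change of wording and one degree of freedom per model. No new data are needed, because a change score already requires the baseline value.

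### Age is used only as ≤ 50 versus > 50, as covariate and as subgroup factor; if its effect is gradual this costs the age comparison roughly 25% to 50% of the linear age information, and the primary estimate almost nothing.

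*SAP*

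**What the plan says.** The same cut, "age (≤ 50 vs. > 50 years"), appears in three places, and no other form of age is planned.

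- SAP, Table 2, primary outcome row, method of analysis: the ANCOVA is "adjusted age (≤ 50 vs. > 50 years), sex and allergy status (yes vs, no").
- SAP, Methods for additional analyses, adjusted analysis if the arms are imbalanced: the "baseline variables in the analysis of covariance: age (≤ 50 vs. > 50 years), sex, and allergy status (yes vs. no").
- SAP, same section, second subgroup analysis: "we will do the same analysis in participants aged ≤ 50 and > 50 years of age".

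The same section says why age matters: "We know that both age and sex will probably affect quality of life and medical care seeking". It also states a direction: "We anticipate that the treatment effect will be larger among both females and younger participants". The method for the subgroups is to set the treatment estimates side by side. For sex the wording is "we will compare the estimates for difference between the mean SNOT-22 scores between the ESS and control groups both in males and females", and age is to be handled in the same way. No interaction test, significance level or power is named for either subgroup question.

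The population is described in the title only as adults. The SAP gives no age limits, mean age or share above 50.

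**The concern.** A two-level age variable treats a 25-year-old and a 50-year-old as alike, and a 50-year-old and a 51-year-old as different. Two things follow if age acts gradually.

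1. **Adjustment.** The SAP chooses ANCOVA to deal with baseline imbalance, and adds an adjusted analysis for imbalance in age. Two arms with equal shares above 50 but different mean ages would look balanced on this covariate, and the chance difference would go unadjusted.
2. **Effect modification.** The SAP expects a larger effect in younger participants. A contrast of two age groups is an inefficient way to examine a gradual trend. The cut loses nothing only if the effect changes abruptly at 50, which the SAP does not claim.

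Most of what is at stake is the second item: how informative the age comparison can be with the participants the trial has.

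**Working it through.** The SAP gives no information, power or sample-size figure on this point, so there is nothing of its own to reproduce.

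**Inputs.** From the SAP: the cut at 50, its use as covariate and as subgroup split, and the expected direction. Assumed: the shape of the age distribution, the share *p* above 50, a linear age effect, the share of outcome variance that age explains (R²), and the starting power of an interaction.

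**Step 1: linear age information kept by the cut.** This is *f*, the squared correlation between age and the indicator of age > 50.

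- Normal age: *f* = φ(z)² / [p(1 − p)], with z the normal quantile at 1 − p. At p = 0.50: 0.3989² / 0.25 = 0.637.
- Uniform age: *f* = 3p(1 − p). At p = 0.50: 3 × 0.25 = 0.75.

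| Age distribution (assumed) | Share above 50 | Kept | Lost |
|---|---|---|---|
| Normal | 50% | 63.7% | 36.3% |
| Normal | 40% | 62.2% | 37.8% |
| Normal | 30% | 57.6% | 42.4% |
| Normal | 25% | 53.9% | 46.1% |
| Normal | 20% | 49.0% | 51.0% |
| Normal | 15% | 42.6% | 57.4% |
| Uniform, 18 to 80 | 48% | 74.9% | 25.1% |
| Uniform, 18 to 70 | 39% | 71.0% | 29.0% |
| Uniform, 18 to 65 | 32% | 65.2% | 34.8% |

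Simulated normal ages truncated to an adult range lose about 31% to 36% with a mean parameter of 50, and about 32% to 61% with 38 to 45. A two-peaked example (peaks at 35 and 60) loses 18%. A true step at 50 loses nothing.

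**Step 2: the age comparison.** Suppose a two-sided 5% test of treatment × linear age has power P. The cut version has power Φ(√f × (1.96 + z_P) − 1.96). For P = 80%, 1.96 + 0.84 = 2.80.

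- Normal, median cut: √0.637 × 2.80 − 1.96 = 0.28, power 61%.
- Uniform, middle cut: √0.75 × 2.80 − 1.96 = 0.47, power 68%.
- Normal, 25% above 50: 54%. Normal, 15% above 50: 45%.

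Matching the continuous-age power takes 1/*f* times the participants: 1.33 (uniform), 1.57 (normal, median cut), 2.35 (normal, 15% above). From a lower start at the normal median cut, 50% falls to 35% and 30% falls to 21%.

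**Step 3: the primary estimate.** The standard error with the cut, relative to linear age, is √[(1 − R² × f) / (1 − R²)].

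- R² = 0.01, *f* = 0.637: √(0.99363 / 0.99) = 1.002, an increase of 0.2%.
- R² = 0.10, *f* = 0.637: √(0.9363 / 0.90) = 1.020, an increase of 2.0%.
- R² = 0.09 (correlation 0.3), *f* = 0.426: √(0.96166 / 0.91) = 1.028, an increase of 2.8%.

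**Step 4: cost of a spline.** A 3-knot restricted cubic spline adds one degree of freedom to the age main effect and one to the interaction. If the truth is linear, the noncentrality stays at 2.80² ≈ 7.85, and a 2-degree-of-freedom test has about 71% power instead of 80%. From a 50% start it has about 40%, against 35% to 40% for the cut. Most of the gain over the cut is then gone, so linear age is the better default.

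**The case against.** The best defence is that the cut is prespecified, stated identically in all three places and easy to read. The reason for 50 may lie in the protocol, which was not available: age group could be a randomisation stratum. That would explain the indicator in the ANCOVA, but it would not prevent adding age in years beside it or modelling effect modification on the continuous scale.

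Several stronger readings are tempting and are not supported.

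- *That at least 36% of the information is lost.* This is the minimum only for normal age with a linear effect. Uniform adult ages give about 25% to 35%, the two-peaked example 18%, and a step at 50 none.
- *That the SAP weakens its own test.* It plans no test of effect modification, only a comparison of estimates. The 80% starting power is illustrative; nothing in the SAP says the trial was sized for an interaction. If true power is low, the age question may stay inconclusive either way.
- *That the primary result is confounded by age.* Allocation is randomised and analysed as randomised, so a coarse covariate leaves the estimate unbiased. Only chance imbalance and a little precision are involved.

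It is also an inference, though a safe one, that age in years is held: the SAP does not say so, but the cut needs it.

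**Conclusion.** The point holds as a low-priority improvement. The SAP uses age in two levels only, without a stated reason, while expecting a directional age effect on benefit. If the relation is gradual, roughly 25% to 50% of the linear age information goes unused, and more if few participants are above 50. The consequence is a less informative age comparison: in the illustration, 80% power becomes 61% to 68%, and less with few above 50. For the primary estimate the consequence is a standard error about 0.2% to 3% larger if age explains 1% to about 10% of outcome variance. No primary conclusion would plausibly turn on that.

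The figures depend on assumed age distributions, a linear age effect and assumed R² values. None of these can be checked from the SAP.

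**What to change.** 1. In Table 2 and in the conditional adjusted analysis, add age in years as a linear covariate. If the ≤ 50 / > 50 grouping was a randomisation stratum, keep that indicator as well.
2. For the age question, estimate treatment × linear age in the full ANCOVA, give the interaction with its 95% CI, and report the treatment effect with 95% CI at two or three ages named in advance. Keep the ≤ 50 and > 50 estimates for display.
3. Optionally, name a 3-knot restricted cubic spline as a sensitivity check on linearity, not as the main model.

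The cost is SAP wording and no new data, provided age in years is on file. The downside is a linearity assumption. The spline relaxes it without removing all assumptions about shape, at the price of the two extra degrees of freedom shown above.

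### The SNOT-22 responder comparison (risk ratio and NNT) is left crude, although the SAP's own reasoning favours baseline control; adjusting would be a cheap gain in a secondary analysis that is valid as it stands

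*SAP*

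**What the plan says.** The section on statistical methods for primary and secondary outcomes defines the primary outcome as the difference in mean SNOT-22 change. It then says that, if baseline averages happen to differ, "comparison of the follow-up scores or change scores will lead to under- or overestimation of the treatment effect". The remedy follows at once: "Therefore, the analysis of covariance will be used where possible baseline imbalances are controlled for". Table 2 gives analysis of covariance for the SNOT-22 mean change and also for the secondary RAND-36 mean change.

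The next row of Table 2, Proportion benefiting, has as its measure "Difference in proportions benefiting (SNOT-22 $>$ MIC) in ESS and control group". The table legend gives "MIC = minimal clinically important change", so the variable is a SNOT-22 change score cut at a threshold. Its whole method is "Chi-squared test, Risk ratio with 95% CI, NNT".

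The section on additional analyses does not reach this row. It says that, if baseline variables are imbalanced, "we also perform adjusted analyses by including the following baseline variables in the analysis of covariance", and lists age, sex and allergy status. That adjustment is confined to analysis of covariance, and baseline SNOT-22 is not in the list.

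**The concern.** The SAP gives a reason for not comparing raw changes between arms, acts on it for two continuous scales, and then compares a dichotomised version of one of those changes in a plain two-by-two table. A participant's chance of passing a cut-off on change depends on the starting score, because participants who start worse tend to improve more on average. If one arm starts worse by chance, its responder proportion rises without any treatment effect.

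Two things are at stake. First, given the baseline difference that the trial actually gets, the crude risk ratio and NNT shift in the direction that the SAP warns about. Secondly, a prognostic score that the trial already collects goes unused, which costs precision. Because "Statistical significance will not be presented for secondary outcomes to avoid multicomparison problem", the estimate and its interval carry the whole message of this row.

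**Working it through.** **Inputs.** The SAP states no MIC value, SD, correlation or sample size, so there is no figure of its own to reproduce. All inputs are assumptions for illustration: SNOT-22 SD 20; baseline to follow-up correlation r = 0.5 (range 0.3 to 0.7); mean improvement 18 points with surgery and 6 in controls; MIC 8; 50 per arm; normal scores.

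**Formulae.**
- SD of change: s = 20 × √(2(1 − r)). At r = 0.5, s = 20.
- A baseline difference d (surgery minus control) adds (1 − r) × d to the mean improvement with surgery.
- Responder probability: Φ((mean improvement − MIC)/s).
- NNT = 1/risk difference.
- Standard error of the baseline difference: 20 × √(2/50) = 4.0 points, so d = ±4 is a one-standard-error imbalance.

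**Results at r = 0.5.** Control: Φ((6 − 8)/20) = Φ(−0.1) = 0.460.

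| d | Surgery | Risk difference | Risk ratio | NNT |
|---|---|---|---|---|
| 0 | Φ(0.5) = 0.691 | 0.231 | 1.50 | 4.3 |
| +4 | Φ(0.6) = 0.726 | 0.266 | 1.58 | 3.8 |
| −4 | Φ(0.4) = 0.655 | 0.195 | 1.42 | 5.1 |

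**Other correlations.** Over d = −4 to +4, the NNT runs from 6.5 to 4.2 at r = 0.3 and from 3.8 to 3.2 at r = 0.7. With MIC 12 and r = 0.5 it runs from 5.1 to 3.7.

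**Size against sampling error.** With balanced baselines, the standard error of the crude risk difference is √(0.691 × 0.309/50 + 0.460 × 0.540/50) = 0.096. The 95% CI is 0.231 ± 1.96 × 0.096, or 0.04 to 0.42, which is an NNT of about 2.4 to 23. The imbalance moves the risk difference by about 0.035, and 0.035/0.096 is about 0.4 standard errors.

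**What adjustment gains.** In 3,000 simulated trials on the same inputs (r = 0.5), the crude risk difference was set beside one standardised from a logistic model with baseline SNOT-22.
- Over all trials, the mean was 0.234 for both.
- Where d was +3 to +5, the crude mean was 0.271 and the adjusted mean 0.235.
- Where d was −5 to −3, the crude mean was 0.197 and the adjusted mean 0.233.
- Correlation with d was 0.40 for the crude estimate and 0.01 for the adjusted one. So about 0.40² = 0.16 of the crude variance tracks the baseline difference.
- The crude variance was about 17% larger. As √1.17 = 1.08, the crude standard error is about 8% larger.

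**The case against.** The strongest reply is that nothing here is invalid. A crude two-by-two comparison in a randomised trial is conventional and transparent, and it is unbiased over randomisations; the equal overall means in the simulation show this. Its confidence interval already allows for chance imbalance, and the shift is small beside that interval. The row is secondary, no significance will be presented for it, and the primary result is a baseline-controlled mean difference. Regression adds some model dependence. All of this stands, and it limits how strongly the point can be put.

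Three stronger readings are tempting, and the document does not support them.
- A reader might infer that the responder estimate is biased. It is off only conditionally, given the imbalance observed in a particular trial.
- A reader might infer that the SAP contradicts itself. The warning stands in the paragraph on the primary outcome and leads to a method for means. The SAP does not mention regression to the mean and does not promise baseline adjustment for every outcome. Carrying its logic over to the cut-off is sound, but it is an inference.
- A reader might infer that any disagreement between the NNT and the primary analysis would come from the missing adjustment. Dichotomising alone can produce disagreement. Moreover, the covariates that Table 2 lists for the primary analysis are age, sex and allergy status, so its conditioning on baseline SNOT-22 has to be read from the text.

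**Conclusion.** The point holds as an improvement to a secondary outcome. The reason that the SAP gives for baseline control applies equally to a thresholded SNOT-22 change, and nothing in the SAP adjusts that row. The crude analysis remains valid; the cost is sensitivity to chance imbalance and some lost precision. On the assumed inputs, a one-standard-error imbalance moves the NNT from 4.3 to 3.8 or 5.1, and the crude variance is about 17% larger. The true size cannot be settled from this document. A weaker correlation between baseline and follow-up makes the shift larger and a stronger one makes it smaller. A 4-point imbalance becomes less likely as the trial grows beyond the assumed 50 per arm.

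**What to change.** In the Proportion benefiting row of Table 2, specify that the risk ratio, risk difference and NNT, each with a 95% CI, come from a binary regression on treatment, baseline SNOT-22 and the covariates of the primary analysis of covariance. Marginal standardisation of a logistic model gives all three; modified Poisson regression would serve for the risk ratio alone. Name baseline SNOT-22 explicitly, because the covariate lists in the SAP do not. Keep the crude counts and percentages by arm beside the adjusted estimates.

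The cost is a line or two of SAP text and one regression on data already collected. The downside is slight dependence on a simple model, which the crude figures let a reader check. The change should be made before the data are seen, since adjustment added afterwards would look post hoc.
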